## 2 PROTOCOL SYNOPSIS

Study Title	Opaganib, a Sphingosine Kinase-2 (SK2) Inhibitor in COVID-19 Pneumonia: a Randomized, Double-blind, Placebo-Controlled Phase 2a Study, in Adult Subjects Hospitalized with SARS-CoV-2 Positive Pneumonia		
Protocol Number	ABC-110		
Sponsor	RedHill Biopharma Ltd.		
Investigational Product	Opaganib (ABC294640)		
Primary Objective	To evaluate the total oxygen requirement (area under the curve) using daily supplemental oxygen flow (L/min) over 14 days (Day 1 to Day 14)		
Secondary Objectives	1) To evaluate the time to 50% reduction from baseline in supplemental oxygen based on oxygen flow in L/min		
	2) To evaluate the proportion of patients no longer requiring supplemental oxygen for at least 24 hours by Day 14		
	3) To evaluate the proportion of afebrile patients at Day 14		
	4) To evaluate the time to negative swabs for SARS-CoV-2 by PCR		
	5) To evaluate the proportion of patients with negative swabs for SARS-CoV-2 by PCR at Day 14		
	6) To evaluate the need for intubation and mechanical ventilation by Day 14		
	7) To evaluate the time to mechanical ventilation		
	8) To evaluate the proportion of patients, with at least one measurement of fever at baseline (defined as temperature >38.0 C[100.4 F]), who are afebrile (defined as temperature <37.2C [99 F]) at Day 14		
	9) To evaluate mortality 30 days post-baseline		
Exploratory Objectives	To assess the change in systemic markers of inflammation (D-dimer, cardiac troponin, C-reactive protein [CRP], lactate dehydrogenase [LDH] and ferritin)		

Safety Objectives	To assess the safety and tolerability of opaganib administered orally at 500 mg Q 12 hours, for up to 14 days, in patients with COVID-19 pneumonia
Study Population	The study population will consist of patients diagnosed with COVID-19 infection who have developed pneumonia defined as radiographic opacities on chest X-ray and require supplemental oxygen. The patients must be hospitalized at least during screening and at baseline (Day 1).
Study Design and Description	This is a phase 2a, proof of concept, multi-center randomized double-blind, parallel arm, placebo-controlled study. The study is planned be performed in US and in other countries, in approximately 15 clinical sites.
	After informed consent is obtained, patients will enter a screening phase for no more than 3 days, to determine eligibility. Approximately 40 eligible patients will be randomized to receive either opaganib added to standard of care, or matching placebo added to standard of care, in a randomization ratio of 1:1. Treatment assignments will remain blinded to the patient, investigator and hospital staff, as well as the sponsor. As there is currently no consensus for a definitive treatment specifically targeting the SARS-CoV-2 virus causing COVID-19 (Wilson, 2020), standard of care will refer to regional, institutional or physician directed therapies, that may be implemented during the COVID-19 pandemic.
	Study participants will receive either opaganib 2 x 250 mg capsules (500 mg) every 12 hours, or matching placebo, in addition to standard of care (pharmacological and/or supportive). Study drug will be administered every day for 14 days (Day 1 to Day 14), unless the patient has been discharged from the hospital without requiring supplemental oxygen, in which case study drug will only be administered to Day 10.
	All participants will be followed up for 4 weeks after their last dose of study drug, which may occur at the end of the 2-week double-blind treatment phase or after premature study drug discontinuation, based upon patient or physician determination.
Stratification	Patients will be stratified based on a minimization algorithm taking the following three parameters into account: age at screening, ≥70 years of age, (yes or no); HbA1c at screening, ≥6.5, (yes or no); oxygen requirement at baseline, requiring non-invasive positive pressure ventilation (e.g. via BIPAP, CPAP), (yes or no)
Treatment	Opaganib 500 mg Q12 hour or matching placebo

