#### **6 BACKGROUND INFORMATION**

#### 6.1 COVID-19 Disease

COVID-19 is a newly recognized disease caused by a coronavirus virus, SARS-CoV-2. A flu-like illness was first noted in December, 2019, in Wuhan, China and was subsequently attributed to a virus similar to the SARS coronavirus, which is now designated as SARS-CoV-2. While the clinical spectrum has not yet been well defined, early reports suggest that SAR-CoV-2 infection ranges from asymptomatic infection to pneumonia and Adult Respiratory Distress Syndrome (ARDS) with multiorgan failure, that may lead to death (Zhou, 2020). In the Zhou study, the median duration of viral shedding was 20 days, with an interquartile range of 17-24 days and a maximum of 37 days. Common symptoms reported in the Zhou study for 191 patients were fever (94%), cough (79%), sputum production and fatigue (each 23%) and myalgia (15%). Bilateral pulmonary infiltrates were noted in 75% of patients on chest X-ray. Patients over 65 years and those with significant comorbidities, such as diabetes, cardiac or pulmonary disease, appeared to be more susceptible for developing severe infection and had a relatively higher mortality rate compared to younger, otherwise healthy patients.

The incidence of symptomatic and severe infection, as a proportion of infected patients, is not yet known, as test availability, utilizing Polymerase Chan Reaction (PCR) performed on nasopharyngeal swabs or other body fluids, has been limited.

For most individuals testing positive, COVID-19 currently appears to be self-limiting. The major threat to this viral pandemic is spread through a nonimmune population, and to those most at risk of severe infection. SAR-CoV-2 is highly contagious, with spread by aerosol and surface contact (van Doremalen, 2020) and potential fecal spread (Chen, 2020). As this is a newly identified disease, first noted in December 2019, and as testing and interpretation of data are in a very early stage, no specific therapy has demonstrated antiviral efficacy.

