# 3.4 Randomization and Blinding

A total of 40 subjects 18 to 80 years old, inclusive will be randomized, using a 1:1 assignment ratio, to treatment with either Opaganib 500 mg Q12 hour (20 subjects) or Placebo (20 subjects), respectively.

A dynamic randomization using the minimization method will be used in this study by Bioforum's DM vendor. Three stratification factors will be used for the minimization algorithm:

- 1. Age at screening,  $\geq 70$  years of age, (yes or no)
- 2. HbA1c at screening,  $\geq 6.5$ , (yes or no);
- 3. Oxygen requirement at baseline, requiring non-invasive positive pressure ventilation (e.g. via PEEP, BIPAP, CPAP, HFNC), (yes or no)

The minimization algorithm will be programmed by Bioforum Ltd using Viedoc system and will employ the Pocock and Simon (Pocock S.J. and Simon R. 1975) methodology with biased coin probability of 0.8 and 'Range' as the variation method. All stratification factors will use the same weight of importance. If the subject meets the eligibility criteria, he or she will be allocated to Opaganib 500 mg Q12 hour or Placebo at 1:1 ratio respectively. Once the enrollment of the subject is approved, the investigator will assign the subject an ID number (subject number) provided by the Viedoc system after running the algorithm on the subject's stratification information.

Treatment assignments will remain blinded to the patient, investigator and hospital staff, as well as the sponsor.

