# 6.3 Demographics and Baseline Characteristics

Demographics and baseline characteristics will be summarized by treatment group and overall using ITT, mITT and Safety populations. Summaries will be presented with the appropriate descriptive statistics as specified in section 5.1 above.

The following will be provided:

- Demographics:
  - Age (years) (continuous)
  - Gender: Male, Female (categorical)
  - Childbearing Potential: Yes, No (categorical, females only)
  - Ethnicity: Hispanic or Latino, Not Hispanic or Latino, Unknown, (categorical)

- Race: White, American Indian or Alaska native, Asian, Black or African American, Native Hawaiian or Other Pacific Islander, Other (categorical)
- Smoking status: Never, Former, Current (categorical), and packyears
- Stratification factors (categorical):
  - Age (years):  $<70, \geq 70$
  - HbA1c at screening:  $<6.5, \ge 6.50$ )
  - Oxygen requirement at baseline requiring non-invasive positive pressure ventilation (e.g. via PEEP, BIPAP, CPAP): yes or no
- Vital signs at baseline, including supplemental oxygen requirement

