### 7.2 Primary Efficacy Endpoint Analysis

The primary analysis will be based on the modified Intent to treat population (mITT), which consist of all patients that were randomized and treated with at least one dose of study drug,

The primary analysis will be based on the baseline-adjusted AUC calculated individually for each subject, as defined in section 3.2.1. Descriptive statistics of the baseline-adjusted AUC will be presented by group and group means will be presented along with 95% confidence interval. The difference in means between the groups will be estimated and presented with 95% confidence interval. Plots presenting individual baseline-adjusted AUC will be presented. Difference between group medians with confidence interval will also be estimated using the Hodges-Lehmann statistics and will be presented along with the non-parametric Wilcoxon rank sum test.

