#### 7.2.1.2 Baseline characteristics adjustment

Estimation of difference between the treatment groups when controlling for the stratification factors and baseline oxygen requirement will be performed, using regression analysis, both for the individual subjects AUC (via Analysis of Covariance) and the group AUC modeling via Repeated measures approach sensitivity analysis.

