#### 7.3 Secondary Efficacy Endpoint analysis

This section describes the analyses to be performed on the secondary efficacy endpoints, as defined in section 3.2.2.

The secondary efficacy endpoints will be analysed using the mITT populations unless otherwise noted for a specific endpoint.

1. Time to 50% reduction from baseline in supplemental oxygen based on oxygen flow in L/min

This time to event will be analyzed as follows: Cox proportional hazards regression model will be used to estimate the hazard ratio (HR) along with 95% confidence interval, comparing Opaganib versus control group. The model will include treatment group as explanatory variable and supplemental oxygen at baseline as covariates. If possible, the stratification factors will also be included as covariates. Kaplan-Meier plot will be provided for illustration of effect (along with median estimates). Cumulative incidence function of the time to 50% reduction from baseline in supplemental oxygen will be estimated using the Kaplan-Meier estimator and will be used to estimate the 14-days cumulative incidence of 50% reduction event for each group, along with 95% confidence interval.

2. The percentage of patients no longer receiving supplemental oxygen for at least 24 hours by Day 14

This binary endpoint ("success"/"failure") will be analyzed as follows: the number of subjects with "success" and "failure" will be summarized using counts and percentages for each group. A 95% confidence interval will be constructed for the proportion of event of interest ("success") in each group. Difference in proportions will be estimated and presented along with 95% confidence interval. Exact confidence intervals will be used as needed (otherwise Wilson (Score) limits will be used). In case loss to follow-up before

event will be recorded, the Cumulative Incidence probabilities at 14-days from the starting of treatment will be estimated using time to event analysis (Kaplan-Meier estimator), censoring loss-to follow up patients at last valid observation date. This analysis will censor death on Day 14.

3. The time to two consecutive negative swabs for SARS-CoV-2 by PCR, at least 24 hours apart

This time to event endpoint will be analyzed using the same methods specified for the first secondary efficacy endpoint (without adjustment for the supplemental oxygen at baseline).

4. The time to two consecutive negative swabs for SARS-CoV-2 by PCR, at least 24 hours apart, followed by continued negative swabs

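### Where the SAP adjusts for age it uses only the ≥70 yes/no minimisation factor; age in years in the supportive AUC models and the Cox models would be a small, cheap gain

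*Protocol*

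**What the plan says.** - **Allocation.** The Protocol Synopsis, Protocol 17.2 and SAP 3.4 name three minimisation factors. The age factor is "age at screening, ≥70 years of age, (yes or no". SAP 3.4 also gives the size and age range: "A total of 40 subjects 18 to 80 years old, inclusive will be randomized".
- **Coding.** SAP 6.3 lists "Stratification factors (categorical" variables, with age as <70 or ≥70. The same section lists "Age (years) (continuous" among the demographics. That descriptive summary is the only place where age in years is used.
- **Primary analysis (SAP 7.2).** No covariates: "The difference in means between the groups will be estimated and presented with 95% confidence interval". A Hodges-Lehmann estimate and a Wilcoxon test accompany it.
- **Adjusted AUC analyses (SAP 7.2.1.2, under sensitivity and supportive analyses).** The treatment difference is estimated "controlling for the stratification factors and baseline oxygen requirement", by ANCOVA and in the repeated-measures model.
- **Cox models (SAP 7.3).** For endpoint 1: "If possible, the stratification factors will also be included as covariates". Endpoints 3, 4 and 6 use the same method without baseline oxygen. No criterion says when inclusion counts as possible.
- **Binary endpoints (SAP 7.3).** Proportions and differences, unadjusted.
- **Background (Protocol 6.1).** "Patients over 65 years and those with significant comorbidities" are described as appearing more prone to severe infection, with relatively higher mortality.

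**The concern.** The protocol itself flags older age as prognostic, yet the models separate patients only at 70. A patient of 69 is treated like one of 20, and patients of 66-69, whom Protocol 6.1 would count as higher risk, fall in the lower group. With 20 per arm, the arms can match on the ≥70 count and still differ in mean age below 70. The adjusted models are there to show whether baseline imbalance explains a treatment difference, and this coding cannot show it inside the <70 group.

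At stake are some precision in the supportive AUC estimates, some protection against chance imbalance there and in the four Cox models, and the stability of the age term in time to intubation or death.

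**Working it through.** **The plan's own figure.** The only stated number is the sample size: 40 × 1/2 = 20 per arm. SAP 3.3 says it was not derived statistically, so there is no power figure to reproduce.

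**Inputs.** From the documents: 40 patients, 20 per arm, ages 18-80, cut at 70. Assumed, because the documents are silent: normal ages truncated to 18-80, with mean 52-70 and SD 11-15 before truncation (realised means about 51-67); age explaining 10% or 20% of AUC variance; event risks of 10-30% for intubation or death.

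**Step 1: age variance kept by the split.** With p the share aged ≥70,

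kept = p(1−p) × (mean age ≥70 − mean age <70)² / Var(age).

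Example, mean 60, SD 12: p = 0.162, subgroup means 74.17 and 55.77, SD after truncation 10.81. Kept = 0.162 × 0.838 × 18.40² / 10.81² ≈ 0.39, so about 61% is lost.

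**Step 2: chance imbalance left after exact balance on ≥70.** SD of the difference in arm mean ages = within-group SD × √(2/20). In the example, 10.81 × √0.606 = 8.42, and 8.42 × 0.316 = 2.66 years.

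**Step 3: precision.** With R² the share of AUC variance explained by age,

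SE ratio (age in years : split) = √[(1−R²) / (1−R² × kept)].

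In the example, √(0.9/0.9606) = 0.968 at R² = 0.10 and √(0.8/0.9212) = 0.932 at R² = 0.20.

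| Mean, SD | Expected ≥70 of 40 | Variance lost | SD of arm difference (years) | SE ratio, R² 10% | SE ratio, R² 20% |
|---|---|---|---|---|---|
| 52, 11 | 1.8 | 80% | 3.0 | 0.958 | 0.913 |
| 52, 15 | 3.5 | 72% | 3.6 | 0.962 | 0.921 |
| 60, 12 | 6.5 | 61% | 2.7 | 0.968 | 0.932 |
| 65, 12 | 10.4 | 51% | 2.3 | 0.973 | 0.942 |
| 70, 11 | 15.6 | 41% | 1.7 | 0.978 | 0.952 |
| 70, 15 | 13.2 | 48% | 2.4 | 0.975 | 0.945 |

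Uniform ages on 18-80 lose 59%. The SE reduction is 2-4% at R² = 10% and 5-9% at R² = 20%.

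This formula ignores the cost of the added term. The ANCOVA has six parameters (intercept, treatment, three factors, baseline oxygen), leaving 34 residual degrees of freedom. A seventh leaves 33, and √(34/33) = 1.015, so roughly 1.5% is given back. At the low end the net gain is close to nil. The formula applies to the linear models only; no comparable figure is claimed for the Cox models.

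**Step 4: time to intubation or death.** The chance of no event among n patients aged ≥70 with event risk q is (1−q)ⁿ.

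| n | q = 10% | q = 20% | q = 30% |
|---|---|---|---|
| 5 | 59% | 33% | 17% |
| 8 | 43% | 17% | 6% |
| 10 | 35% | 11% | 3% |

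The model has four terms (treatment and three factors). With 10-30% of 40 patients having events there are 4-12 events, or 1-3 per term. An age term without a finite estimate is therefore realistic for this endpoint.

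**The case against.** The strongest reply is that little depends on this. The primary comparison and the binary endpoints have no age term. The adjusted AUC models are supportive, and SAP 5.3 says nominal p-values will not be read inferentially. Adjusting for minimisation factors as coded in the allocation is standard. A linear age term brings its own assumption, and Protocol 6.1 describes a threshold at 65, not a slope. All of this stands, and it keeps the point minor. It does not remove it, because age in years is already collected and SAP 5.3 leaves readers to judge the overall pattern of estimates.

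The variance share is also assumed. Baseline oxygen, HbA1c and ventilation need are already in the AUC models, so what age adds to them could be smaller than 10-20%. That stands too.

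Four stronger readings are tempting and not supported:

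- **That most age information is discarded.** This depends on a distribution that the documents do not give. The loss is about half at an assumed mean of 65 and below half at 70.
- **That every time-to-event model may lose its age term through an event-free older group.** Endpoints 1, 3 and 4 count favourable events (oxygen reduction, negative swabs), and nothing in the documents suggests that these are rare. The argument fits endpoint 6 only.
- **That an event-free group spoils the treatment estimate.** The age coefficient diverges, but the treatment hazard ratio normally remains estimable. Adjustment is lost only if the analyst drops the term under the undefined condition. That condition covers HbA1c and ventilation need equally and is a separate gap.
- **That age imbalance shifts an odds ratio for intubation or death by a stated factor.** The SAP plans no odds ratio: endpoint 5 is an unadjusted difference in proportions and endpoint 6 a hazard ratio.

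**Conclusion.** The point holds as a minor improvement to the supportive AUC models and the four Cox models. It is established from the text that these models use age only as <70 or ≥70, that the Cox models include it conditionally, and that age in years is available but unused in modelling.

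The size rests on assumptions: about 40-80% of age variance lost, a residual chance difference in mean age with SD about 2-3.5 years, and an SE smaller by about 2-9% before the cost of one extra term. A dropped age term is a realistic risk for time to intubation or death only.

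**What to change.** Leave the minimisation and the primary analysis as they are.

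- **SAP 7.2.1.2:** add age in years as a linear covariate beside the stratification factors, in both the ANCOVA and the adjusted repeated-measures model.
- **SAP 7.3, Cox models for endpoints 1, 3, 4 and 6:** name age in years as the age covariate in place of the ≥70 indicator. The number of terms stays the same, which matters where events are few, and the estimate no longer depends on events occurring in one small group.

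The cost is a sentence in each section, one degree of freedom in the AUC models, a linearity assumption, and an age term in the Cox models that no longer matches the minimisation coding exactly. The change belongs in the SAP before unblinding. If the codes have already been opened, these analyses should be reported as post hoc.

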#### **Study Duration**

Recruitment period is estimated at 3 months

The maximum duration of study participation will be up to 45 days (including up to 3 days screening; 2 weeks double-blind (DB) treatment phase and 4-weeks off-study drug follow-up)

### Eligibility Criteria

#### Inclusion:

- 1) Adult male or female  $\ge 18$  to  $\le 80$  years of age
- 2) Proven COVID-19 infection per RT-PCR assay of a pharyngeal sample (nasopharyngeal or oropharyngeal) AND pneumonia defined as radiographic opacities on chest X-ray
- 3) The patient requires supplemental oxygen at baseline
- 4) The patient, guardian or legal representative has signed a written IRB-approved informed consent
- 5) Male participants with female partners of child-bearing potential agree to one of the following methods of contraception during the treatment period and for at least 1 month after the last dose of study drug:
  - Abstinence from penile-vaginal intercourse and agree to remain abstinent.
  - Male condom, with female partner using a highly effective contraceptive method. (For further details regarding highly effective contraceptive methods please see section 9.3.)

In addition, male participants must refrain from donating sperm for the duration of the study and for 1 months after last dose of study drug.

Male participants with a pregnant or breastfeeding partner must agree to remain abstinent from penile-vaginal intercourse or use a male condom during each episode of penile penetration for at least 1 months after the last dose of study drug Female participants:

A female participant is eligible to participate if she is:

- a) not pregnant
- b) not breastfeeding
- c) not a woman of child-bearing potential (WOCBP, as defined in Section 9.3)
- d) a WOCBP who agrees to use a highly effective method of contraception consistently and correctly during the treatment period and for at least 1 months after the last dose of study drug (please see further details on Section 9.3).

#### Exclusion:

- 1. Any co-morbidity that may add risk to the treatment in the judgement of the investigator.
- 2. Requiring intubation and mechanical ventilation
- 3. Patient having a do not intubate or do not resuscitate order
- 4. Oxygen saturation ≥95% on room air
- 5. Any preexisting respiratory condition that requires intermittent or continuous ambulatory oxygen prior to hospitalization
- 6. Patient is, in the investigator's clinical judgement, unlikely to survive >72 hours
- 7. Pregnant (positive serum test within 3 days prior to randomization) or nursing women
- 8. Unwillingness or inability to comply with procedures required in this protocol.
- 9. Corrected QT (QTc) interval on electrocardiogram (ECG) >470 ms for females or >450 ms for males, calculated using Friedericia's formula (QTcF)
- 10. AST (SGOT) or ALT (SGPT) > 5.0 x upper limit of normal (ULN)
- 11. Bilirubin >2.0 x ULN (except where bilirubin increase is due to Gilbert's Syndrome)
- 12. Serum creatinine >2.0 X ULN
- 13. Absolute neutrophil count <1000 cells/mm^3
- 14. Platelet count <75,000/mm^3
- 15. Hemoglobin < 8.0 g/dL
- 16. Currently taking medications that are sensitive CYP3A4, CYP1A2, CYP2C9, CYP2C19 or CYP2D6 substrates and have a narrow therapeutic index. These should be decided in discussion with the Medical Monitor on a case-by-case basis.
- 17. Currently taking medications that are strong inducers or inhibitors of CYP2D6 and CYP3A4. These should be decided in discussion with the Medical Monitor on a case-by-case basis.
- 18. Currently taking warfarin, apixaban, argatroban or rivaroxaban.
- 19. Current drug or alcohol abuse

[figure not shown]
	20. Currently participating in a clinical study assessing pharmacological treatments, including anti-viral studies	
Number of Subjects	Up to approximately 40 subjects will be randomized	
Number of Investigator Sites	Approximately 15 participating hospital centers	
Screening/Basel ine Assessments	
 
Signed informed consent
 
Eligibility determination
 
Complete medical history (including onset of COVID-19 symptoms)
 
Concomitant medication assessment
 
Baseline review of systems
 
Physical examination
 
Vital signs (temperature, blood pressure, pulse rate, respiratory rate and oxygen saturation by pulse oximeter)
 
Weight if the patient is ambulatory
 
Oxygen requirement (L/min)
 
12-lead electrocardiogram
 
Chest Xray
 
Nasopharyngeal or oropharyngeal swab for SARS-CoV-2 PCR test
 
Serum chemistry
 
CRP, D-Dimer, LDH, ferritin, cardiac troponin
 
HbA1c
 
CBC with differential
 
	
	• Urinalysis	

	Serum pregnancy test (for women of childbearing potential) within 3 days prior to treatment	
Study Assessments	The following will be monitored and documented daily as part of the standard ocare:	
	Concomitant medications	
	Adverse Events	
	Interim Physical exam	
	Vital signs (temperature, blood pressure, pulse rate, respiratory rate and oxygen saturation by pulse oximeter)	
	Oxygen requirement (L/min)	
	The following will be monitored less frequently as part of standard of care and wherever possible:	
	• For patients on concomitant hydroxychloroquine, a 12-lead electrocardiogram (if allowed by hospital treatment guidelines under COVID-19) approximately 3 hours after the first study drug administration on Day 1, anytime on Days 2 and 4, and again at end-of-treatment (either Day 10, 14 or at premature study drug discontinuation). If patients are on monitors (including telemetry or Holter monitors), investigators are encouraged to collect QT interval data	
	Nasopharyngeal or oropharyngeal viral swab for SARS-CoV-2 PCR test every 1-3 days	
	Serum chemistry once weekly	
	Serum CRP, D-Dimer, LDH, ferritin, cardiac troponin once weekly	
	CBC with differential once weekly	
	Chest X-ray as per physician decision	
Study Endpoints	Primary	
	The total oxygen requirement (area under the curve) using the daily supplemental oxygen flow (L/min) over 14 days (Day 1 to Day 14)	
	Secondary	
	1) Time to 50% reduction from baseline in supplemental oxygen based on oxygen flow in L/min	

2) The percentage of patients no longer receiving supplemental oxygen for at least 24 hours by Day 14 3) The time to two consecutive negative swabs for SARS-CoV-2 by PCR, at least 24 hours apart 4) The percentage of patients with at least two consecutive negative swabs, followed by continued negative swabs, for SARS-CoV-2 by PCR at Day 14 5) The percentage of patients requiring intubation and mechanical ventilation by the end of the 2-week off-study-drug follow-up 6) The time to intubation and mechanical ventilation 7) The percentage of patients with at least one measurement of fever at baseline (defined as temperature >38.0 C[100.4 F]), who are afebrile (defined as temperature <37.2C [99 F]) at Day 14 8) Mortality due to any cause at Day 30 **Exploratory** 1) The mean change in systemic markers of inflammation (D-dimer, cardiac troponin, C-reactive protein [CRP], procalcitonin [PCT], lactate dehydrogenase [LDH] and ferritin) from baseline at Day 14 **Safety** 1) Incidence rates of all treatment-emergent AEs (TEAEs) and SAEs 2) Evaluation of vital signs 3) Evaluation of laboratory parameters (chemistry and hematology) 4) Evaluation of electrocardiograms (ECG) Sample Size The sample size for this Proof of Concept study was not chosen for statistical Estimation consideration, as there are no formal statistical inferences planned. The size of the study is judged adequate for the preliminary evaluation objectives. Statistical The primary efficacy objective of the study is to evaluate the effect of Opaganib on total supplemental oxygen requirement (area under the curve) using daily Methods oxygen flow (L/min) measurements for 14 days (Day 1 to Day 14). The primary efficacy endpoint will calculate for each patient the area under the curve of the supplemental oxygen requirement through day 14, using the trapezoidal rule after subtracting the baseline oxygen requirement at each day. Days where no supplementary oxygen was needed, will be recorded as 0. If several values of

oxygen requirement (L/min) are recorded in a certain day, for the primary analysis the highest of these values will be taken. In the primary analysis, for patients who die before Day 14, or require intubation and mechanical ventilation, missing daily values will be assigned the maximal supplemental oxygen flow requirement of 8L/min. For patients discharged from hospital on supplemental oxygen prior to Day 14, if no values are collected by the site after discharge, the oxygen requirement (L/min) on the day of discharge will be assigned thereafter for each day to Day 14. The primary analysis will be based on the modified Intent to treat population (mITT), which consist of all patients that were randomized and treated with at least one dose of study drug, Descriptive statistics of the baseline-adjusted AUC will be presented by group along with 95% confidence interval for each group and for the difference in means between the groups. It is planned to collect supplemental oxygen requirement up to Day 14 even if a patient discontinues treatment prior to Day 14 but continues in the study to Day 14. Further, it is assumed that loss to follow up such that vital status up to Day 14 will be missing is unlikely. Therefore, the primary analysis will assume that in case that all supplemental oxygen values are missing after treatment discontinuation, the last value is carried forward - until Day 14, or death, if occurred before. A sensitivity analysis to the above missing data handling approach will be performed using an AUC summary statistics approach, in which groups AUC is calculated from the estimated parameters of a Repeated-Measures model.

